**11.5.4.5. Laboratory Parameters**

Laboratory Parameters

 
Non-quantifiable laboratory results will be treated as missing in summary displays. However, the results will be listed as received (e.g. '<x' or '>x').
 
An 'any visit post-baseline' classification will be derived, in which subjects will be counted in the 'low' and 'high' categories if they reported a low or high value (respectively) at any scheduled or
 

Laboratory Parameters

unscheduled on-treatment visit.
 
 
Change from baseline values will be classified relative to the normal range as ‘to low’, ‘to normal or no change’ or ‘to high’. Subjects who do not change categories or move from out-of-range to normal will be classified as ‘to normal or no change’.
 
An ‘any visit post-baseline’ change classification will be derived, in which subjects will be counted in the ‘to low’ and ‘to high’ categories if they reported a change from a ‘normal’ baseline to a value below or above the normal range (respectively) at any scheduled or unscheduled on-treatment visit. Subjects who did not report a change to a value outside the normal range at any visit after the start of study treatment will be counted in the ‘to normal or no change’ category.
 

Multiple Measurements for Post-Baseline Visits for Safety

 
Subjects having both high and low values relative to normal ranges at post-baseline visits for safety parameters will be counted in both the high and low categories of the “any visit post-baseline” row of related summary tables.
 

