**11.5.4.4. Maximum/Minimum Post-Baseline and Worst-Case Post-Baseline**

Maximum/Minimum Post-Baseline and Worst-Case Post-Baseline	
Definition	Reporting Details
Maximum post-baseline (QTcF, QTc B, PR interval, ECG heart rate, pulse rate, systolic BP, diastolic BP and laboratory tests)	Maximum on-treatment value over all time-points (including scheduled and unscheduled assessments)
Minimum post-baseline (Diastolic BP and laboratory tests that do not have a lower limit = 0)	Minimum on-treatment value over all time-points (including scheduled and unscheduled assessments)
Worst case post-baseline (ECG findings)	
Including scheduled and unscheduled on-treatment assessments
 
 
'Abnormal' if any on-treatment assessment is evaluated as 'Abnormal'
 
'Unable to evaluate' if all on-treatment assessments are 'Unable to evaluate'
 
'Normal' if any on-treatment assessment is evaluated as 'Normal' and there are no on-treatment assessments evaluated as 'Abnormal'
 

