## 11.6. Appendix 6: Handling of Missing Data

Element	Reporting Detail
General	
 
• Missing data occurs when any requested data is not provided, leading to blank fields on the collection instrument:               
 
○ These data will be indicated by the use of a “blank” in subject listing displays unless all data for a specific visit are missing in which case the visit is not displayed in the listing.
 
○ Answers such as “Not applicable” and “Not evaluable” are not considered to be missing data and will be displayed as such.
 
○ Missing data will generally not be considered in the calculation of percentages (i.e., the denominator will not include subjects who have missing data at a given time point).
 
○ No imputation will be made for any missing numerical data, except in the specified sensitivity analyses of the primary and secondary endpoints to assess the impact of missing data on study results.
 
 
 

Responder	
 
• Subjects with a missing baseline will have responder status as missing.
 
• Subjects with missing on-treatment data and a subsequent non-missing on-treatment scheduled assessment will not be considered a responder or non-responder but will be left as missing.
 
• Subjects that have withdrawn from study treatment prior to the visit in question will be imputed as non-responders at all visits post-study treatment discontinuation where the assessment was expected to be performed (regardless of whether the subject has had a post-treatment assessment performed or not). This includes all visits up to and including Week 52.
 
• Subjects with missing on-treatment data and no subsequent non-missing on-treatment scheduled assessments will be imputed as non-responders.
 

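### Lab results beyond the assay limit ('<x' or '>x') are set to missing in summaries, so known extremes drop out of the maximum/minimum and 'any visit' displays and can be counted as no change

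*SAP*

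**What the plan says.** The governing sentence in SAP 11.5.4.5 is "Non-quantifiable laboratory results will be treated as missing in summary displays". The next sentence adds "However, the results will be listed as received" and gives both '<x' and '>x' as examples. The SAP does not separate results below the limit from results above it. It substitutes no limit value and does not say that a high or low flag is kept.

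These rules act on the result once it is missing:

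- **Maximum (SAP 11.5.4.4):** "Maximum on-treatment value over all time-points (including scheduled and unscheduled assessments"), for laboratory tests among others.
- **Minimum (SAP 11.5.4.4):** the scope is "Minimum post-baseline (Diastolic BP and laboratory tests that do not have a lower limit = 0").
- **'Any visit' high/low (SAP 11.5.4.5):** subjects are counted in the low and high "categories if they reported a low or high value (respectively) at any scheduled or" unscheduled on-treatment visit.
- **'Any visit' change (SAP 11.5.4.5):** 'to low' and 'to high' need a move out of range from a normal baseline. "Subjects who did not report a change to a value outside the normal range at any visit after the start of study treatment" go to 'to normal or no change'.
- **Missing data (SAP 11.6):** "No imputation will be made for any missing numerical data, except in the specified sensitivity analyses" of the primary and secondary endpoints, and "Missing data will generally not be considered in the calculation of percentages".

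**The concern.** A '>x' result tells the analyst that the true value lies above x. Setting it to missing discards that knowledge at the point where it matters most. Hematology and clinical chemistry parameters are a stated safety endpoint (Protocol 6.3; SAP 2.2). Several displays exist to show extremes: the liver-function trellis, the maximum and minimum scatter and box plots (Figures 3.18 to 3.26), and the tables of values and changes relative to the normal range (Tables 3.061, 3.062, 3.065 and 3.066). SAP 11.5.4.4 brings unscheduled and treatment-discontinuation assessments into the maximum and minimum. The rule in 11.5.4.5 then removes any of those results that went past the assay limit.

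The 'any visit' change row goes further than omission. Its third category is a default, so a subject whose one abnormal result has been set to missing is positively assigned to it. The arm comparison would then show no change for a subject who may have the largest value in the trial.

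**Working it through.** The plan gives no figure on this point to reproduce. The check is to follow one subject through the rules. The values below are assumed for illustration and are not in the documents. The visits are the on-treatment laboratory visits in Protocol 6.3.12.

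**Assumed inputs:** normal range 10 to 40; assay upper limit 1000; baseline 30; Week 16 = 38; Week 28 = '>1000'; Week 52 = 35.

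1. **Apply SAP 11.5.4.5.** Week 28 becomes missing in summaries. SAP 11.6 allows no imputation, so the usable on-treatment values are 38 and 35.
2. **Maximum post-baseline (11.5.4.4).** max(38, 35) = 38, and 38/40 = 0.95 times the upper limit of normal. The true value exceeds 1000/40 = 25 times that limit.
3. **'Any visit' high.** No usable value exceeds 40, so the subject is not counted.
4. **'Any visit' change.** Baseline 30 is normal and no usable value is out of range, so the subject falls to 'to normal or no change'. The correct entry is 'to high'.
5. **Week 28 by-visit row.** The subject generally leaves the denominator and is not called normal.

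The low side mirrors this. A '<x' result, with x at or below a non-zero lower normal limit, is lost from the minimum and from the 'low' and 'to low' counts.

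**Conditions for step 4.** All of the following must hold:

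- The baseline is normal. A subject already high at baseline cannot become 'to high' under this rule, however '>x' is handled. A missing baseline gives no derivation at all (SAP 11.4.2).
- x lies at or beyond the normal limit.
- No other on-treatment value is out of range.

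Steps 2 and 3 do not need a normal baseline. Step 3 still needs every other on-treatment value to be at or below the upper limit. Step 2 needs only that the result beyond the limit was the subject's largest.

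**Results that are not affected in this way.** A '<x' result for a test whose lower limit is 0 is within range, and such tests are already outside the minimum display.

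**The case against.** The strongest reply is that safety capture does not rest on these summaries. Out-of-limit results are listed as received. Protocol 6.3.3 has clinically significant laboratory abnormalities recorded as adverse events. Large ALT elevations trigger 24-hour reporting and liver event forms (Protocol 6.3.1 and 6.3.11), with their own summary (Table 3.057). The adverse events of special interest include hyperglycaemia and effects on potassium. Laboratory data are summarised descriptively, with no modelled treatment comparison. All of this stands, and it limits the consequence. It does not correct a wrong count in a table or an understated point in a figure, and those are the displays that set the arms side by side. The listing safeguard is also not fully secured. Listings 26 and 27 cover subjects with at least one value outside the normal range, and the SAP does not say whether a subject whose only such value is non-quantifiable would be selected.

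A second reply is that the 'any visit' rules speak of what a subject reported, which could be read to include '>x'. The SAP does not say so, and its sentence on missing values points the other way. If that reading is intended, it needs to be written down.

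A reader might infer that the rule works only in the direction that hides abnormality. The documents do not support that. Dropping '<x' results pushes means upward, and for tests where high values are the worry, such as ALT or bilirubin, that makes an arm look worse. A reader might also infer that every '>x' result is tabulated as normal. That happens only in the 'any visit' change row, under the conditions listed above.

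**Conclusion.** The rule is wrong as written, and neither document contains text that overrides it. Its effect is confined to descriptive laboratory tables and figures: the maximum and minimum displays, the 'any visit' high and low counts, and the default category of the 'any visit' change row. By-visit percentages lose the subject from the denominator. No efficacy conclusion depends on it.

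The size cannot be computed. The documents give no assay limits, no analytes for which limits are reached, and no frequency of such results. A percentage bias in group means could be produced only by assuming a share of values beyond the limit and a distribution, and it would say nothing about this trial. Such results may be rare, but displays meant to show rare extremes are where a single lost value matters.

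The conclusion assumes that the missing-value sentence is applied literally to every laboratory summary, including the derived maximum, minimum and category variables.

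**What to change.** Replace the sentence in SAP 11.5.4.5 with a rule in three parts:

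1. **Categories.** A '>x' result with x at or above the upper normal limit is classified as high. A '<x' result with x at or below a non-zero lower normal limit is classified as low. This applies in the by-visit, 'any visit' and change-category derivations.
2. **Numerical summaries.** The limit value x is used for both '>x' and '<x' in the maximum, minimum and continuous summaries, with a footnote that these values are censored at the assay limit.
3. **Listings.** Results stay as received, and Listings 26 and 27 select subjects with the same classification as part 1.

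The cost is one replaced passage in the SAP and one derivation step in the laboratory dataset. The small downside is that substituted values are approximate for means: x understates a '>x' result and overstates a '<x' result. Part 1 matters most and does not carry that cost.

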3.050	ITT	Summary of On-treatment Pneumonia Incidence Resulting in Hospitalization/Prolonged Hospitalization or Death	SAC
3.051	ITT	Summary of On-treatment Details of Pneumonia Resulting in Hospitalization/Prolonged Hospitalization or Death	SAC
Composite Endpoints			
3.052	ITT	Summary and Analysis of Time to First On-treatment Event in the Pneumonia AESI Group or On-treatment Moderate/Severe COPD Exacerbation	SAC
3.053	ITT	Summary and Analysis of Time to First On-treatment Severe COPD Exacerbation or On-treatment Event in the Pneumonia AESI Group Resulting in Hospitalization/Prolonged Hospitalization or Death	SAC
3.054	ITT	Summary and Analysis of Time to First On-treatment Severe COPD Exacerbation or On-treatment Event in the Cardiovascular AESI Group Resulting in Hospitalization/Prolonged Hospitalization or Death or On-treatment Event in the Pneumonia AESI Group Resulting in Hospitalization/Prolonged Hospitalization or Death	SAC
Bone Fractures			
3.055	ITT	Summary of On-treatment Bone Fractures	SAC
Radiography (Chest Imaging)			
3.056	ITT	Summary of On-treatment Chest Imaging (X-ray or CT Scan)	SAC
Liver Event			
3.057	ITT	Summary of Liver Monitoring/Stopping Event Reporting	SAC
3.058	ITT	Summary of Hepatobiliary Laboratory Abnormalities	SAC
Laboratory Parameters			
3.059	ITT	Summary of Chemistry Data	SAC
3.060	ITT	Summary of Change from Baseline in Chemistry Data	SAC
3.061	ITT	Summary of Chemistry Data Outside the Normal Range	SAC

Safety Tables			
No.	Popu- lation	Title	Deliverable [Priority]
3.062	ITT	Summary of Chemistry Changes from Baseline Relative to the Normal Range	SAC
3.063	ITT	Summary of Hematology Data	SAC
3.064	ITT	Summary of Change from Baseline in Hematology Data	SAC
3.065	ITT	Summary of Hematology Data Outside the Normal Range	SAC
3.066	ITT	Summary of Hematology Changes from Baseline Relative to the Normal Range	SAC
Vitals Signs			
3.067	ITT	Summary of Vital Signs	SAC
3.068	ITT	Summary of Change from Baseline in Vital Signs	SAC
3.069	ITT	Analysis of Pulse Rate (bpm)	SAC
3.070	ITT	Analysis of Systolic Blood Pressure (mmHg)	SAC
3.071	ITT	Analysis of Diastolic Blood Pressure (mmHg)	SAC
ECGs			
3.072	ITT	Summary of ECG Values	SAC
3.073	ECG	Summary of ECG Values	SAC
3.074	ITT	Summary of Change from Baseline in ECG Values	SAC
3.075	ECG	Summary of Change from Baseline in ECG Values	SAC
3.076	ITT	Summary of ECG Findings	SAC
3.077	ECG	Summary of ECG Findings	SAC

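### The any-visit laboratory change row has no category for a subject who crosses from low to high, or from high to low (SAP 11.5.4.5)

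*SAP*

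**What the plan says.** SAP 11.5.4.5 (Laboratory Parameters) holds all the relevant rules.

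- **Change at a visit.** There are three categories: 'to low', 'to normal or no change' and 'to high'. The middle one is defined as follows: "Subjects who do not change categories or move from out-of-range to normal will be classified as" 'to normal or no change'. No condition is placed on the baseline category.
- **Change at any visit, 'to low' or 'to high'.** A subject is counted "if they reported a change from a ‘normal’ baseline to a value below or above the normal range (respectively"). Planned and unplanned on-treatment visits both contribute.
- **Change at any visit, 'to normal or no change'.** This takes: "Subjects who did not report a change to a value outside the normal range at any visit after the start of study treatment".
- **Multiple measurements.** "Subjects having both high and low values relative to normal ranges at post-baseline visits for safety parameters will be counted in both". What is meant is that such a subject enters the high category and also the low one in the any-visit row of related tables.
- **Absolute low or high at any visit.** This is a separate classification. It counts subjects "if they reported a low or high value (respectively) at any scheduled or" unscheduled on-treatment visit, whatever the baseline.

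The change rules feed Table 3.062, titled "Summary of Chemistry Changes from Baseline Relative to the Normal Range", and Table 3.066, its hematology counterpart (SAP 11.12.7).

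**The concern.** An any-visit row should collect everything that the visit rows show. Here it uses a narrower definition than the visit rows above it, and its third category does not take up those whom the narrower definition leaves out. A subject can be 'to high' at Week 28 and appear nowhere in the any-visit row of the same table.

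The unscheduled case adds to this. SAP 11.4.3 keeps unscheduled visits out of summary tables, apart from maximum, minimum or worst-case assessments and baseline. A crossing seen only at an unscheduled visit therefore has no visit row, and the any-visit row is the only place in the change table where it could be counted.

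A programmer who codes the third category as the remainder would instead report a crossing of the whole normal range as 'to normal or no change'. The SAP wording does not permit that, but it is an easy way to make the row add up.

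**Working it through.** The plan states no figure to reproduce. The check applies the two change rules literally to every possible combination.

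**Inputs.** The rules are from SAP 11.5.4.5. Baseline is the last value before first dose (SAP 11.4.2). The scheduled on-treatment laboratory visits are Weeks 16, 28 and 52 (Protocol 6.3.12).

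**One visit: 3 baseline states × 3 visit states = 9 combinations.**

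| Baseline | Visit | Visit rule | Any-visit rule |
|---|---|---|---|
| low | low | to normal or no change | to normal or no change |
| low | normal | to normal or no change | to normal or no change |
| low | high | to high | **none** |
| normal | low | to low | to low |
| normal | normal | to normal or no change | to normal or no change |
| normal | high | to high | to high |
| high | low | to low | **none** |
| high | normal | to normal or no change | to normal or no change |
| high | high | to normal or no change | to normal or no change |

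The rules agree in 7 of 9. The other 2 have a category at the visit and none in the any-visit row.

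**Three visits: 3 × 3³ = 81 paths.**

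- Normal baseline: all 27 paths are placed.
- Low baseline: a path is unplaced if at least one visit is high, which is 27 − 2³ = 19 paths.
- High baseline: 19 by symmetry.
- Unplaced in total: 38 of 81.
- Of these, paths with both a low and a high value after baseline: 2 × (27 − 8 − 8 + 1) = 24. The multiple-measurements bullet might place them.
- Paths with post-baseline abnormal values on one side only: 2 × (2³ − 1) = 14. No rule places these.

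These are counts of possible paths, not of expected subjects.

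**Example of one of the 14.** Baseline low, Week 16 normal, Week 28 high, Week 52 normal. The Week 28 row counts the subject as 'to high'. The any-visit row does not count the subject at all.

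**When the any-visit count falls below a visit's count.** At Week 28, let n subjects go from normal to high and m from low to high. Let k be the normal-baseline subjects who are high only at other visits. The Week 28 'to high' count is n + m and the any-visit count is n + k. The any-visit count is the lower one when k < m. That can happen but need not; the m subjects are missing from the any-visit row either way, apart from any that the bullet is taken to place.

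**After the change below.** With the any-visit row derived from the visit rule, none of the 81 paths is unplaced.

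**The case against.** **A normal baseline may be intended.** A row for new abnormality arising from normal is a reasonable display, since the absolute classification already counts every abnormal value. But the visit rule carries no such restriction, and the third any-visit category excludes the crossing subjects instead of receiving them. The SAP gives no reason for the difference. That reading would require changes to the other two rules as well.

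**The multiple-measurements bullet may cover the gap.** It covers part at most. It needs both high and low values after baseline, so it cannot reach the 14 one-sided paths. Its categories are named high and low, as in the absolute classification, and whether it governs the change tables is unclear. If it did, a low-baseline subject with later low and high values would be counted on both sides, although no visit was 'to low'.

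**The information is not lost from the report.** This stands. A crossing at a scheduled visit is in that visit's row. The abnormal value is counted in the any-visit part of the out-of-range tables (3.061, 3.065). It also enters the plots of maximum and minimum post-baseline values against baseline (Figures 3.19, 3.21, 3.23, 3.25), and Listings 26 and 27.

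**Conclusion.** The rule is wrong as written, and the consequence is minor. The any-visit row of Tables 3.062 and 3.066 is inconsistent with the visit rows of those tables. The conclusion rests on a literal reading of SAP 11.5.4.5 and on no numerical assumption.

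A reader might infer more than the documents support:

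- **That headline results are affected.** SAP 11.12.2 reserves that term for displays marked SAC [1]. Both tables are marked SAC only.
- **That a potassium or glucose safety signal is hidden.** The special-interest groups for potassium and hyperglycaemia (SAP 11.5.4.2) are built from coded adverse-event terms and do not use this row.
- **That the largest changes are dropped.** Crossing both limits is a change of category, not a measure of size. A normal value rising to several times the upper limit can be a bigger change, and it is counted.
- **That the number of subjects can be stated.** Assuming 1–3% low at baseline and 5–30% high later, 10,000 × 0.01 × 0.05 = 5 and 10,000 × 0.03 × 0.30 = 90 per analyte. Neither rate is in the documents, and the second should be conditional on a low baseline. The range does not carry over between analytes: SAP 11.5.4.4 recognises tests with a lower limit of 0, for which a low value should not arise. Such crossings are probably uncommon, but that too is an assumption.

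No imbalance between arms follows from the rule, and no test uses these tables.

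**What to change.** In SAP 11.5.4.5, delete the normal-baseline condition and derive the any-visit change row from the visit rule, applied to every scheduled and unscheduled on-treatment visit:

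- count a subject as 'to low' or 'to high' if any such visit is so classified, and in both if both occur;
- count a subject as 'to normal or no change' only if no visit is classified 'to low' or 'to high'.

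It would help to add that the multiple-measurements bullet does not override this in the change tables. Under the visit rule a subject can be in both categories only from a normal baseline.

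Every subject with a baseline and an on-treatment value then has a category, and the any-visit count cannot be lower than that of any on-treatment visit. The cost is one SAP sentence and a small program change, with no new data and no effect on any other display. It is best made before unblinding.

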**11.5.4.6. ECG**

ECG Event Rates			

 
ECG Abnormality event rates will be calculated in the same manner as AE rate.
 
			
ECG Categories			
QTcF and QTcF change from baseline results will be reported in categories as below			
ECG Parameter	Units	Ranges	
		Lower	Upper
Absolute			
Absolute QTcF Interval	msec	0	≤ 450
		> 450	≤ 480
		> 480	≤ 500
		> 500	≤ 530
		> 530	
Change from Baseline			
Change from Baseline QTcF	msec		<-60
		≥-60	<-30
		≥-30	<0
		≥0	< 30
		≥ 30	<60
		≥ 60	

**11.5.4.7. Pneumonia**

Pneumonia
Pneumonia Event Rates
Pneumonia event rates (based on the pneumonia eCRF form) will be calculated in the same manner as AE rate.
Association of Chest X-Ray with Pneumonia Event

 
Pneumonia is considered to be supported by a chest X-ray if there is an associated X-ray which shows the presence of infiltrates. A chest X-ray is considered associated with pneumonia if it is performed within the duration of the pneumonia or performed between -7 to +10 days (inclusive) of the date of onset of pneumonia.
 

